4.1.2 Exclusion Criteria

A subject will be excluded if one or more of the following conditions apply:

1. Breast-feeding or planning to become pregnant during the study.

Subject has received any of the following substances:

2. More than 10 days of systemic immunosuppressive medications or cytotoxic medications within the 4 weeks prior to enrollment or any within the 14 days prior to enrollment
3. Blood products within 16 weeks prior to enrollment
4. Live attenuated vaccines within 4 weeks prior to enrollment
5. Inactivated vaccines within 2 weeks prior to enrollment.
6. Investigational research agents within 4 weeks prior to enrollment or planning to receive investigational products while on the study
7. Current allergy treatment with allergen immunotherapy with antigen injections, unless on maintenance schedule
8. Current anti-TB prophylaxis or therapy
9. Previous H2 influenza investigational vaccine
10. Receipt of a licensed influenza vaccine within 6 weeks before trial enrollment

Subject has a history of any of the following clinically significant conditions:

11. Serious reactions to vaccines that preclude receipt of study vaccinations as determined by the investigator
12. Hereditary angioedema, acquired angioedema, or idiopathic forms of angioedema
13. Asthma that is not well controlled
14. Diabetes mellitus (type I or II), with the exception of gestational diabetes
15. Thyroid disease that is not well controlled
16. Idiopathic urticaria within the past year
17. Evidence of autoimmune disease or immunodeficiency
18. Hypertension that is not well controlled
19. Bleeding disorder diagnosed by a doctor (e.g. factor deficiency, coagulopathy, or platelet disorder requiring special precautions) or significant bruising or bleeding difficulties with IM injections or blood draws
20. Malignancy that is active or history of malignancy that is likely to recur during the period of the study.
21. Seizure disorder other than 1) febrile seizures, 2) seizures secondary to alcohol withdrawal more than 3 years ago, or 3) seizures that have not required treatment within the last 3 years
22. Asplenia, functional asplenia or any condition resulting in the absence or removal of the spleen
23. Guillain-Barré Syndrome
24. Psychiatric condition that precludes compliance with the protocol; past or present psychoses; or within 5 years prior to enrollment, a history of suicide plan or attempt

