4.2.3 Enrollment and Randomization

Day 0 is defined as the day of protocol enrollment and first injection for all groups. Protocol-specific eligibility is reviewed on Day 0 as part of the enrollment process, but eligibility evaluations conducted during a screening visit are routinely used for eligibility if evaluations are within the specified window prior to Day 0. However, if clinical assessment on Day 0 suggests significant changes may have occurred since the screening visit, then evaluations done on Day 0 are used for eligibility. Day 0 evaluations and medical history prior to the first injection are the baseline for subsequent safety assessments.

Part I includes staged enrollment with required interim safety reviews before proceeding with the next dose group. In Group 1, five subjects will be enrolled with no more than one subject per day. Following dose escalation review, five subjects will be enrolled in Group 2 with no more than one subject per day. An internal safety review will determine whether enrollment can begin in Part II.

In Part II subjects will be stratified by age and randomized equally into Group 3 and Group 4. Neither the clinic staff nor the subjects will know in advance which group will be assigned to the enrollees in the study. The Protocol Statistician will prepare the randomization plan in advance and provide it to the site Pharmacy and Data Management Center.

The pharmacy database and study randomization will be set up prior to opening the study to accrual. The group assignment will become known to the staff and subject immediately after completing the electronic enrollment into the study on Day 0. The visit schedule is based on intervals of time after each study injection (Appendix II).

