4.2.4 Administration of Study Vaccines

All study injections will be completed according to the assigned group and vaccines will be administered IM in the deltoid muscle. Blood draws must be completed before vaccinations.

On the injection day (prior to injection), study subjects will be clinically evaluated and samples will be collected as per Schedule of Evaluations (Appendix II). A subject who arrives at the clinic with fever or evidence of an acute illness that precludes administration of the vaccine may be rescheduled within the allowed study visit window.

Pregnancy test results for women of reproductive potential must be obtained on each injection day prior to the study injection and the results must be negative to proceed.

When choosing an arm for injection, clinicians should consider whether there is an arm injury, local skin problem or significant tattoo that precludes administering the injection or will interfere with evaluating the arm after injection.

Subjects enrolled in Group 1, Group 2, and Group 3 will be observed for a minimum of 1 hour. Vital signs (temperature, blood pressure, pulse and respiratory rate) will be collected at least 1 hour after the injection, prior to subject departure from the clinic. Subjects enrolled in Group 4 will be observed for a minimum of 30 minutes; vital signs will be collected after at least 30 minutes. The injection site will be inspected for evidence of local reaction.

Subjects randomized in Group 3 will receive the DNA A/Sing prime vaccine with the needle-free injection device, PharmaJet. The PharmaJet device requires that the DNA A/Sing product be administered as two 0.5 mL injections. When the PharmaJet device is used, subjects and clinicians will be asked to wear safety glasses during product administration. (See Section 8.5.2)

In keeping with the NIH CC policy and good medical practice, acute medical care will be provided to subjects for any immediate allergic reactions or other injury resulting from participation in this research study.

4.2.5 7-Day Solicited Reactogenicity and Follow-up

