APPENDIX II: SCHEDULE OF EVALUATIONS

VRC 500		VRC 316 Schedule of Evaluations PART I: Group 1										
Visit Number	*01	02	02A	03	04	05	06	08	10	11		
Week of Study	-12 to 0	W0	W1	W1	W2	W4	W16	W18	W28	W40		
Day of Study	-84 to 0	1D0	D1	D6	D14	D28	D112	D126	D196	D280		
Clinical	Tube											
*VRC 500 Screening Consent	X											
VRC 316 AoU; Consent		X										
2Physical exam for eligibility, height /weight/ vitals at screening; vital signs and targeted exam (as needed) other visits.	X	X		X	X	X	X	X	X	X		
Medical history targeted to eligibility at screening; then interim medical history	X	X		X	X	X	X	X	X	X		
3Study Product Administration:		HA-F A/Sing										
Part I, Group 1												
Phone evaluation (clinic visit as needed)		X										
Begin diary card		X										
4Pregnancy test: urine or serum	X	X				X				X		
4Pregnancy prevention counseling/ Reproductive Information Form	X	X				X				X		
CBC with differential	3	3			3	3				3		
Iron	X					X						
Total bilirubin, AST, ALT, and ALP	4	4			4	4				4		
Creatinine	X	X		4								
5HLA type						20						
HIV (other tests, if needed)	4											
Research Samples												
H. pylori ferritin antibody and Human ferritin antibody	X					X						
Antibody assays. Serum storage	32	32		32		32	32	16	32	32		
Immunological assays (T cell and antibody responses). PBMCs and plasma storage	80	80		80		80	80	40	80	80		
Daily Volume (mL)	123	119	0	116	7	139	112	56	112	119		
Max. Cumulative Volume (mL)	123	242	242	358	365	504	616	672	784	903		

* VRC 500: Most screening evaluations must be no more than 84 days prior to Day 0 to be used for eligibility (pregnancy test from Day 0 must be used for eligibility). If clinical assessment on Day 0 suggests significant changes may have occurred since screening, then physical examination & laboratory studies done on Day 0 are used for eligibility.

¹ Day 0=day of enrollment and first vaccine injection. Day 0 evaluations prior to first injection are the baseline for assessing adverse events subsequently.

² Screening visit includes physical exam with vital signs. At other visits, physical examination is done if indicated by interim history or laboratory test results. Otherwise only blood pressure (BP), pulse, and temperature are required.

³ Study Product Administration: Part I: Group 1 will receive HA-F A/Sing 20 mcg IM at Day 0. Complete post vaccination evaluations (BP, pulse, temperature, respiration and injection site assessment) at 1 hour or longer after study injection.

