³ Study Product Administration: Part II: Group 3A/B will receive DNA A/Sing HA-F A/Sing 4 mg IM at Day 0 and HA-F A/Sing 60 mcg IM at Week 16. Complete post vaccination evaluations (BP, pulse, temperature, and injection site assessment) at 1 hour or longer after each study injection. Group 4A/B will receive HA-F A/Sing 60 mcg IM at Day 0 and at Week 16. Complete post vaccination evaluations (BP, pulse, temperature, respiration and injection site assessment) at 30 minutes or longer after each study injection.

⁴ Negative pregnancy test results must be confirmed for women of reproductive potential prior to each study injection.

⁵ HLA type blood sample is collected once at any time-point in the study and is shown as a Visit 05 evaluation for convenience; however, if HLA type is already available in the medical record, it does not need to be repeated. HLA type may also be obtained from a frozen sample.

⁶ Visit 07: Two tubes of PBMCs collected in EDTA tubes will be sent to Building 40, while the remainder of the blood collected will be sent to VITL.

⁷ If optional apheresis occurs, ONLY draw 32mL in SST (DO NOT draw 120 mL in EDTA tubes). For women of reproductive potential, pregnancy test must be negative within 72 hours prior to apheresis procedure.

Visit windows: Schedule Visits 02A through 06 with respect to Day 0; Schedule Visits 06A through 11 with respect to Visit 06. The following visit windows apply: Visits 02A and 06A (+1 day). Visit 03 and 07 (±1 day). Visits 04, 05 and 09 (±2 days). Visit 06 (±28 days). Visits 08 (±3 days). Visits 10 and 11 (±14 days).

**APPENDIX III: ASSESSMENT OF RELATIONSHIP TO VACCINE AND GRADING
SEVERITY OF ADVERSE EVENTS**

Assessment of Relationship of an Adverse Event to Study Vaccine:

The relationship between an AE and the vaccine will be assessed by the investigator on the basis of his or her clinical judgment and the definitions below.

- **Definitely Related.** The AE and administration of study agent are related in time, and a direct association can be demonstrated.
- **Probably Related.** The AE and administration of study agent are reasonably related in time, and the AE is more likely explained by study agent than other causes.
- **Possibly Related.** The AE and administration of study agent are reasonably related in time, but the AE can be explained equally well by causes other than study agent.
- **Not Related.** The AE is clearly explained by another cause not related to the study product.

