 Modified from FDA Guidance - September 2007**

A. Tables for Clinical Abnormalities

Local Reaction to Injectable Product	Mild (Grade 1)	Moderate (Grade 2)	Severe (Grade 3)	Potentially Life Threatening (Grade 4)
Pain	Does not interfere with activity	Repeated use of non-narcotic pain reliever > 24 hours or interferes with activity	Any use of narcotic pain reliever or prevents daily activity	Hospitalization
Tenderness	Mild discomfort to touch	Discomfort with movement	Significant discomfort at rest	Hospitalization
¹ Erythema/Redness	2.5 – 5 cm	5.1 – 10 cm	> 10 cm	Necrosis or exfoliative dermatitis requiring medical attention
² Induration/Swelling	2.5 – 5 cm and does not interfere with activity	5.1 – 10 cm or interferes with activity	> 10 cm or prevents daily activity	Necrosis requiring medical attention
³Vital Signs	Mild (Grade 1)	Moderate (Grade 2)	Severe (Grade 3)	Potentially Life Threatening (Grade 4)
⁴ Fever (°C) (°F)	38.0 – 38.4 100.4 – 101.1	38.5 – 38.9 101.2 – 102.0	39.0 – 40 102.1 – 104	> 40 > 104
Tachycardia - beats per minute	101 – 115	116 – 130	> 130	Hospitalization for arrhythmia

⁵ Bradycardia - beats per Minute	50 – 54	45 – 49	< 45	Hospitalization for arrhythmia
Hypertension (systolic) - mm Hg	141 – 150	151 – 155	> 155	Hospitalization for malignant hypertension
Hypertension (diastolic) - mm Hg	91 – 95	96 – 100	> 100	Hospitalization for malignant hypertension
Hypotension (systolic) – mm Hg	85 – 89	80 – 84	< 80	Hospitalization for hypotensive shock
Respiratory Rate – breaths per minute	17 – 20	21 – 25	> 25	Intubation

1. In addition to grading the measured local reaction at the greatest single diameter, the measurement should be recorded as a continuous variable.
2. Induration/Swelling should be evaluated and graded using the functional scale as well as the actual measurement.
3. Subject should be at rest for all vital sign measurements.
4. Oral temperature; no recent hot or cold beverages or smoking.
5. When resting heart rate is between 60 – 100 beats per minute. Use clinical judgment when characterizing Bradycardia among some healthy subject populations, for example, conditioned athletes.

Systemic (General)	Mild (Grade 1)	Moderate (Grade 2)	Severe (Grade 3)	Potentially Life Threatening (Grade 4)
Nausea/vomiting	No interference with activity or 1 – 2 episodes/24 hours	Some interference with activity or > 2 episodes/24 hours	Prevents daily activity, requires outpatient IV hydration	Hospitalization for hypotensive shock

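### Respiratory rate is graded on absolute cut-offs after injection, but no pre-injection reading is required that day, and the Group 3 footnote omits it after injection as well

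*Combined protocol and SAP*

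**What the plan says.** **Grading.** The vital-sign table in Appendix III uses absolute values. The row "Respiratory Rate – breaths per minute" sets Grade 1 at 17-20, Grade 2 at 21-25 and Grade 3 above 25. The row "Hypertension (systolic) - mm Hg" sets Grade 1 at 141-150, Grade 2 at 151-155 and Grade 3 above 155. Among the modifications listed in Appendix III, the exemption for values inside the institutional normal range covers laboratory values only. Bradycardia alone has a resting-rate qualifier and an allowance for clinical judgment.

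**Entry.** Section 4.1.1 asks for good general health and an examination without clinically significant findings. Section 4.1.2 excludes "Hypertension that is not well controlled". Neither gives a number for blood pressure, pulse or respiratory rate.

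**Baseline.** Section 4.2.3: "Day 0 evaluations and medical history prior to the first injection are the baseline for subsequent safety assessments".

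**Before injection.** Footnote 2 of each Appendix II table: "Screening visit includes physical exam with vital signs". For other visits it makes a physical examination conditional on history or laboratory results, and continues: "Otherwise only blood pressure (BP), pulse, and temperature are required".

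**After injection.** Section 4.2.4, for Groups 1 to 3: "Vital signs (temperature, blood pressure, pulse and respiratory rate) will be collected at least 1 hour after the injection". For Group 4 it asks for vital signs after at least 30 minutes. Footnote 3 lists respiration for Groups 1, 2 and 4. For Group 3 it reads: "Complete post vaccination evaluations (BP, pulse, temperature, and injection site assessment) at 1 hour or longer after each study injection".

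**Analysis.** Adverse events of all severities to the Week 4 visit after each injection are a primary endpoint (section 6.3.1). Section 6.5.3 covers reactogenicity, adverse events and laboratory values, and has no summary of vital signs.

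**The concern.** An eligible subject may already sit at a graded value before vaccination. The way to tell such a value from a new one is to compare it with the subject's own pre-injection reading. The plan requires that reading for blood pressure, pulse and temperature. It does not require it for respiratory rate, whose Grade 1 band begins at 17 breaths per minute.

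Two things are at stake. First, a graded respiratory rate after injection cannot be classed as new or pre-existing from data that the plan requires that day. Second, if the Appendix II footnotes are followed as written, Group 4 has respiration checked after each injection and Group 3 does not. A difference between randomized arms in respiratory findings could then come from how they were observed.

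**Working it through.** **1. The plan's own figures.** The documents give no expected rate of vital-sign events. The nearest figures are in section 6.4.1 and Table 6-1, and they reproduce. With Pr(0) = (1-p)^n, n = 10 and p = 0.2: 0.8^10 = 0.107, and Pr(more than 1) = 1 - 0.107 - 10(0.2)(0.8^9) = 0.624, as printed. Every cell agrees to within 0.0005. The 90% thresholds are 0.369 and 0.021 for n = 5, and 0.206 and 0.010 for n = 10, also as printed. The plan's arithmetic is not in question.

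**2. Where respiratory rate is required.**

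| Time | Section 4.2.4 | Appendix II footnotes |
|---|---|---|
| Screening (up to 84 days before) | not covered | vital signs, not itemised |
| Before injection, Day 0 and Week 16 | clinical evaluation, refers to Appendix II | not required unless an examination is indicated |
| After injection, Groups 1 and 2 | yes | yes |
| After injection, Group 3 | yes | not listed |
| After injection, Group 4 | vital signs at 30 minutes or later | yes |

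In Part II, with 20 subjects per arm and two injections each, the footnotes give 20 x 2 = 40 required post-injection respiratory readings in Group 4 and none in Group 3. Section 4.2.4 gives 40 in each.

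**3. Readings inside the adverse-event windows.** For Groups 2 to 4, each injection has a post-injection reading and three visits (Days 6, 14 and 28, then Days 118, 126 and 140). That is 2 x 4 = 8 systolic readings. Required respiratory readings number 2 where respiration is collected. Group 1, with one injection, has 4 and 1.

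**4. Without a distribution.** A subject with a steady rate of 18 shows a Grade 1 value after both injections with no change at all. If one reading is graded with probability q, the chance over two readings lies between q (perfectly correlated) and 1-(1-q)^2 (independent): 5% to 10% for q = 5%, 20% to 36% for q = 20%, 50% to 75% for q = 50%.

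**5. With assumed distributions and no vaccine effect.** All means and SDs here are assumptions; the documents give none. Each reading is a subject mean plus within-subject noise, rounded, with 200,000 simulated subjects per scenario. For one reading, q = 1 - Φ((c - 0.5 - mean)/√(between² + within²)), where c is the cut-off. For example, with c = 17, mean 15 and both SDs 1.5: 1 - Φ(1.5/2.12) = 24%. The rows below are the lowest, a middle and the highest scenario.

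| Measure | Mean / between SD / within SD | One reading graded | Any graded | Any graded and Day 0 ungraded |
|---|---|---|---|---|
| Systolic ≥141, 8 readings | 115 / 8 / 6 | 0.5% | 2.8% | 2.5% |
| | 120 / 10 / 8 | 5.5% | 20.6% | 16.4% |
| | 125 / 12 / 9 | 15.1% | 41.8% | 28.4% |
| Respiratory ≥17, 2 readings | 14 / 1 / 1 | 3.8% | 6.8% | 5.4% |
| | 15 / 1.5 / 1.5 | 24.1% | 36.8% | 20.9% |
| | 16 / 1.5 / 1.5 | 40.8% | 56.9% | 25.0% |

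The last two columns are shares of all subjects. Systolic Grade 3 (above 155) runs from 0.02% to 9%.

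Of the 45 subjects planned for Groups 2 to 4, the any-graded shares are about 1 to 19 for systolic pressure and 3 to 26 for respiratory rate, or 2 to 14 of 25 for respiratory rate if Group 3 has no reading.

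**6. What a Day 0 respiratory rate would add.** In the middle scenario, 36.8% - 20.9% = 15.9% of subjects have a graded post-injection rate that was already graded at Day 0. In the highest it is 56.9% - 25.0% = 31.9%. The required data cannot now identify them.

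**7. The two arms.** If graded readings were recorded as events and the footnotes were followed, no vaccine effect would give about 0.068 x 20 = 1 to 0.569 x 20 = 11 subjects with a respiratory event in Group 4, and none in Group 3.

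**The case against.** A reader might infer that many subjects will have a vital-sign adverse event with no vaccine effect. The documents do not support that. Section 5.1 says that each adverse event is graded; it does not say that each gradable reading is an adverse event, and an investigator may judge that a steady rate of 18 is not one. The rates above depend on that recording step and on assumed distributions. A result that runs from a few percent to over half shows how much the assumptions decide.

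Nor does the plan lack a baseline. Day 0 is named, and blood pressure, pulse and temperature are required then. A respiratory rate may also exist from screening, since section 4.2.4 counts it among vital signs, or from an examination that was indicated. Entry also screens on general health and examination findings. A reader might further expect the noise to fall mainly on ages 52-70; the documents hold no data on that, and randomization is stratified by age.

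The consequences are limited too. Unsolicited events carry attribution, are tabulated by severity and relationship, and are listed in full. The pause rule for them needs the same related event at Grade 3 or higher in two subjects (section 4.5.1).

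All of this stands. It does not touch two gaps: no required respiratory rate on the injection day before injection, and the conflict over Group 3.

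**Conclusion.** The point holds as two gaps in data collection and one in reporting. Post-injection respiratory rate has no required same-day comparator, although the plan names Day 0 as its safety baseline. Section 4.2.4 and the Group 3 footnote disagree on whether respiration is recorded after injection, and the Group 4 footnote includes it. No vital-sign summary uses the baseline readings that are taken. These conclusions rest on the text alone.

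The size is conditional. If gradable readings were recorded as events, the no-effect share would be 7% to 57% for respiratory rate and 3% to 42% for systolic pressure under the stated assumptions. Neither range is a forecast. This is an inexpensive improvement to a sound safety plan and does not put the primary endpoint in doubt.

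**What to change.** 1. In footnote 2 of each Appendix II table, add respiratory rate to the vital signs taken before each injection.
2. Reconcile section 4.2.4 with the Group 3 text in footnote 3, so that the same vital signs are recorded in both Part II arms.
3. In section 6.5.3, add a table by group of change in each vital sign and shift in grade from the Day 0 pre-injection reading, alongside the adverse-event tables. Show change from the boost-day pre-injection reading as well. Day 0 should stay the main reference, because a boost-day baseline alone could hide a lasting change after the prime. Note in the table that the post-injection reading falls at 1 hour or later in Group 3 and 30 minutes or later in Group 4.

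Keep every single reading in the listings, and do not make a confirmatory repeat a condition for counting an adverse event. In a first-in-human study, that condition could remove real but transient post-injection changes from the count.

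The cost is one extra breath count per injection visit and one extra table.
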